7.6 Stopping Rules

No stopping rules for the study have been developed by the Sponsor. The Principal Investigator is responsible for suspending study enrollment for reasons of subject/clinician safety and well-being.

8.0 STUDY POPULATION

Healthy male and female volunteers, 18 years of age or older, with no dermatological conditions or known history of sensitivity to natural rubber latex, adhesive skin products (e.g., Band-Aids, medical tapes), polyester, Octenidine Dihydrochloride, or common personal care or beauty products will be enrolled into this study. A sufficient number of volunteers will be enrolled, such that a minimum total of 24 readings for the groin (sebaceous rich) region and 24 readings for the abdominal (sebaceous poor) region are evaluable for the Investigation Product (test article) and Negative Control arms; a minimum total of 24 readings for the groin region and 24 readings for the abdominal region are evaluable for the Vehicle Control arm and a minimum total of 24 readings for the groin region and 24 readings for the abdominal region are evaluable for the Saline Control arm

Subjects must satisfy all Treatment Day Inclusion/Exclusion Criteria prior to Treatment Day procedures. Subjects may qualify on the abdominal and/or inguinal sites and be admitted into testing for one or both anatomical sites, although if more subjects qualify for treatment than can be treated in a given time period, preferential admittance into the treatment phase will be given to subjects qualifying in both the

abdominal and inguinal test areas. To be included in the primary analysis (mITT data set), a treatment site must have a Treatment Day microbial baseline equal to or greater than the stated minimum requirement. Enrollment will continue until minimum number of subjects meeting baseline criteria on each body region per treatment arm is identified.

A minimum of 36 human subjects will be treated utilizing bilateral applications to ensure that the treatments will be evaluated on the sites as described in the following table. Each subject has four independent sampling sites: left and right sides for the abdomen and left and right sides for the groin.

Table 4.0: Estimated No. of readings per anatomical site (abdomen and groin), per treatment, per sampling interval (10-minutes)			
Arm	Treatment	Number of Abdomen Evaluations	Number of Groin Evaluations
Test article	Thermally treated polyester cloth impregnated with 0.4% w/v octenidine dihydrochloride	24	24
Vehicle Control	Thermally treated polyester cloth impregnated with vehicle formulation	24	24
Saline control	0.9% normal saline applied with polyester cloth	24	24

Unless specified otherwise, these criteria apply at screening and throughout the study.

8.1 Inclusion Criteria

Individuals that satisfy all of the following conditions will be considered for participation:

- a. Males and/or females, at least 18 years or older and of any race.
- b. Are in good general health.
- c. Unable to become pregnant, or willing to use an acceptable method of contraception (i.e. oral contraception, intra-uterine device [IUD], diaphragm, condom, abstinence, bilateral Tubal ligation, or are in a monogamous relationship with a partner who has had a Vasectomy) to prevent pregnancy for at least 14 days immediately preceding Treatment Day and throughout the duration of the study, if female of child-bearing potential.
- d. All female subjects must have a negative urine pregnancy test on Treatment Day prior to any applications of the study products.
- e. Have skin within 6 inches of the test sites that is free of dermatoses, abrasions, cuts, lesions or other skin disorders.
- f. Cooperative and willing to follow Subject Instructions (Appendix 22.6).
- g. Cooperative and willing to sign Consent Form and HIPAA Authorization Form.
- h. Able to read, write and follow instructions in English.

8.2 Exclusion Criteria

Subjects with any one of the following characteristics will be excluded from participation in this study:

- a. Exposure to topical or systemic antimicrobials or any other product known to affect the normal microbial flora of the skin, antibiotics or steroids (other than hormones for contraception or post-menopausal reasons) exposure within 14 days prior to Treatment Day and for the remainder of the study. Restrictions include, but are not limited to antimicrobial-containing soaps, antiperspirants/deodorants, shampoos, lotions, perfumes, after shaves, and colognes.
- b. Swimming in chemically treated pools or bathing in hot tubs, spas and whirlpools within 14 days prior to Treatment Day and for the remainder of the study.
- c. Use of tanning beds, hot waxes, or depilatories, including shaving (in the applicable test areas) within 14 days prior to Treatment Day and for the remainder of the study.
- d. Contact with strong detergents, solvents, acids, bases, bug repellent, fabric softener-treated clothing, UV treated clothing or other household chemicals in the applicable test areas within 14 days of the Treatment Day and for the remainder of the study.
- e. Subjects who have a history of sensitivity to vinyl, natural rubber latex, adhesive skin products (e.g., Band-Aids, medical tapes), polyester, metals, inks, common antibacterial agents found in common personal beauty or personal care soaps, lotions, or ointments particularly octenidine dihydrochloride.
- f. Subjects who have asthma requiring medication, diabetes, hepatitis B or C, an organ transplant, mitral valve prolapse with a heart murmur, congenital heart disease, lupus, Crohn's disease, medicated multiple sclerosis, internal prosthesis or any immunocompromised conditions (such as AIDS or HIV positive).
- g. Subjects who have a history of skin allergies.
- h. Subjects who have a history of skin cancer within 6 inches of the applicable test areas or have received treatment for any type of internal cancer within the 5 years prior to enrollment.
- i. Any tattoos or scars on the test sites or within 2 inches of the test sites; skin blemishes or warts may be permissible with the specific approval of the Principal Investigator or consulting physician.
- j. Dermatoses, cuts, lesions, active skin rashes, scabs, breaks in the skin or other skin disorders within 6 inches on or around the test sites.
- k. A currently active skin disease or inflammatory skin condition (for example contact dermatitis; psoriasis, and eczema) anywhere on the body.
- l. Subjects who are pregnant, attempting pregnancy, or nursing.
- m. Subjects who have showered or bathed within at least 72 hours of the Treatment Day (sponge baths may be taken, however, the lower abdomen and upper thigh region must be avoided).
- n. Subjects who receive an irritation score of 1 (any redness, swelling, rash, or dryness present at any treatment area) for any individual skin condition prior to the Treatment Day baseline sample collection.
- o. Participation in another clinical trial in the 30 days prior to signing the informed consent for this study, current enrollment in another clinical trial, or have already participated in this study.

8.3 Subject Selection

Number of Subjects

A sufficient number of male and female, overtly healthy volunteer subjects at least 18 years of age, will be enrolled to ensure that the total number of evaluable samples collected from groin and abdominal regions are not less than 24 evaluable tests per anatomical site from each treatment arm (minimum of 24 each for groin and abdominal regions). A minimum of 36 evaluable subjects is required to achieve a total of at least 24 test sites for groin and abdominal regions. Subjects must satisfy all Treatment Day Inclusion/Exclusion Criteria prior to Treatment Day procedures. If the required numbers of subjects do not qualify from the initial screening group, additional volunteers will be recruited. At least 4 male or female, overtly healthy volunteer subjects at least 18 years of age will be utilized for the neutralization study.

Based upon historical microbial baseline counts, approximately 76 subjects will be screened such that sufficient subjects are treated to meet the requirement for 24 evaluable treatment sites for each treatment arm on abdomen and groin. The three study products will be assigned for bilateral applications blocks of 24 subjects to assure that each product is evaluated on the skin of each anatomical site – the abdomen and the inguen – at each post-treatment sample time from at least 36 subjects meeting treatment day baseline requirements.

Subject Recruitment

Following approval of the Study Protocol, Informed Consent Form, and other study specific documents by the IRB and Sponsor, potential subjects will be recruited. Personal information will be collected for each potential subject, using the Subject Confidential Information and Acceptance Criteria Form (SCIAC form, Form 15-SR-004). Each consenting subject will fill out an Informed Consent Form (ICF) and the Authorization to Use and Disclose Protected Health Information Form (HIPAA form, Form 15-SR-008). A List of Restricted Products will be provided to each subject prior to beginning the study (Form SR-002-113016). The above forms are provided as separate Informed Consent documents. During the consenting process, emergency contact information of individuals who can be contacted, should any problem arise, will be collected for each participant. Trained personnel or subject recruiters will explain the study to each subject, review the elements of Informed Consent as specified in 21 CFR 50.25, and determine subject eligibility through direct questioning, and will be available to answer any questions that may arise. It will be made clear to subjects that their participation in this study will accrue to them no personal benefits, other than financial compensation, as stated. The Informed Consent Form will be signed and dated by the subject and the person obtaining consent prior to the start of any study procedures. The subject will receive a copy of the signed Informed Consent Form. Subjects will be notified that additional information about this study may be found at www.clinicaltrials.gov.

The subject recruiters will verbally verify with subjects that the skin of the abdomen and inguen are free from clinically evident dermatoses, injuries, or any other disorders that may compromise the subject or the study.

Potential subjects will be informed of volunteer opportunities available at the investigative site by means of general, nonspecific newspaper and radio advertisements instructing potential subjects to either read IRB-approved study descriptions online or in person. Additionally, subjects may be recruited from existing subject database, referrals, through response to advertising and from community outreach and events. All study-specific advertising materials will be approved by the IRB prior to their use for recruiting subjects.

9.0 DESCRIPTION OF STUDY PRODUCTS

9.1 Test Product(s)

The materials identified in Table 5.1 will be used in the study. Specific product lot numbers will be included on separate Investigational Product (study materials) release/receipt form provided by the sponsor with the shipment of the materials.

Study Arm	Treatment Code	Name	Lot No.	Exp.
Test Article	A or B	Thermally treated polyester cloth impregnated with 0.4% w/v octenidine dihydrochloride	TBD	TBD
Vehicle Control	A or B	Thermally treated polyester cloth impregnated with vehicle formulation	TBD	TBD
Saline Control	C	0.9 % normal saline applied with polyester cloths	TBD	TBD

*BD will supply the polyester cloth for the saline control. BSL will purchase 0.9% normal saline.

9.2 Equipment

The equipment used during this study will be detailed on Clinical Trials Equipment Tracking Forms, and the forms will be included in the Final Report.

9.3 Supplies

The supplies used during this study will be detailed on Clinical Trials Supplies Tracking Forms, and the forms will be included in the Final Report.

9.4 Media

Sterile Sampling Solution (SS):

Butterfield's Phosphate Buffered Water (PBW):

312 µM KH₂PO₄, pH 7.2 ± 0.1

Tryptic Soy Agar with product neutralizers (TSA+) – may be purchased or made by BSL

9.5 Product Labeling

BD will label, package and ship the study materials to the research facility. Test article and vehicle control materials will be labeled randomly assigned blinded codes A or B prior to shipment to BSL.

The polyester cloth for saline application will be labeled with code C. BSL personnel will document receipt and storage of study materials using the assigned code.

Investigational products (or the immediate packaging) shall be labeled in accordance with regulatory requirements, including the following statement: "CAUTION-Investigational product. Limited by Federal (or United States) law to investigational use."

Commercial products will be supplied as labeled by the manufacturer.

9.6 Maintenance and Storage of Study Products

The test materials will be received and stored by BSL in accordance with instructions from the Sponsor and BSL procedures and retained in secure quarantine when not being used in testing. BSL will maintain an inventory of the test materials in secure quarantine and a log of use. Unused, sealed test materials will be stored by BSL until the Sponsor specifies its disposition. In the absence of a disposition request from the Sponsor within 1 year of planned usage, the test materials will be returned to the Sponsor. No test materials will be destroyed unless requested by the Sponsor. Lot Numbers and Expiration dates will be provided by the Sponsor with each product shipment. The unblinded lot numbers of the Investigational Products and Active Control will be provided to BSL by the Sponsor at the completion of the study when unblinding has occurred.

10.0 STUDY PROCEDURES

Procedure	Timing		
	14 days or more prior to Treatment	3 or more days prior to Treatment	Treatment Day
Informed Consent Obtained	X		
Product-Restriction Period	X	X	
Inclusion/Exclusion Criteria including Medical History Reviewed	X	X	X
Clipping Hair From Test sites		X	
Pregnancy Test			X

Test-Day Baseline Sample		X
Product Application		X
10-Minute Post-Product Application Sample		X
Adverse Events	X	X

Note: Visual evaluations of the skin on each test area will be performed at each laboratory visit prior to treatment, and prior the 10-minute post-treatment microbial sampling.

Note: All sampling times will be calculated from the completion of the dry time of each product following application.

10.1 Enrollment

The Inclusion/Exclusion Criteria will be reviewed with each subject to ensure eligibility for the study. Prior to the scheduled Treatment Day, subjects will undergo a minimum 14-day washout period. The subjects will be instructed to avoid contact with any topical or systemic antimicrobial products for the duration of their involvement in the study as written in the Subject Instructions. If it becomes necessary to take systemic antibiotics or to apply topical medications to the test areas within this pretreatment period, the subject must contact the Investigator as soon as reasonably possible so that another volunteer may be recruited.

Restrictions include, but are not limited to:

- Use of antimicrobial containing soaps, shampoos, lotions, perfumes, after shaves or powders, colognes, antiperspirants, deodorants
- Contact with materials such as acids, bases, solvents, bug repellent, fabric softener-treated clothing, UV treated clothing or other household chemicals
- Swimming in chemically treated pools and bathing in hot tubs, spas and/or whirlpools
- Use of tanning beds, hot waxes or depilatories (including shaving)

Subjects will be provided a kit with non-antimicrobial personal care products for exclusive use during the study. Subjects will also be provided with written instructions regarding the use of these products.

Subjects will be asked about the condition of the skin at the test areas and their response will be documented. All subjects will be scheduled to return to the test facility approximately 96 hours before the Treatment Day for an initial visual assessment of the test areas and hair removal from the sites to facilitate sample collection, if required.

Subjects will be required to refrain from bathing or showering for at least 72 hours prior to Treatment Day.

Sponge bathing will be allowed, however, the subject must avoid the lower abdomen and upper thigh region.

10.2 Pre-Treatment Day

At least 4 days (96 hours) prior to Treatment Day, the Investigator or a designee will complete the Pre-Treatment Day Inclusion/Exclusion Criteria page in each subject's source document CRF. If these criteria are satisfied, a visual skin assessment will be performed to evaluate the condition of each test area and hair will be clipped, if required.

Subjects will be required to refrain from bathing or showering at least 72 hours prior to Treatment Day.

10.3 Treatment Day

The Investigator or a designee will complete the Treatment Day Inclusion/Exclusion Criteria source/CRF. If these criteria are satisfied, subjects will don a disposable undergarment and a visual skin assessment will be performed to evaluate the condition of each test area.

The randomization schedule will designate the treatment to each side of the abdomen and groin.

10.3.1 Preparation of Abdominal Test Area on Treatment Day

The test site within the abdominal region (abdominal test area) is defined as the area to the right and left sides of the abdomen, adjacent to the umbilicus that appear to be similar in condition and above the groin. Using a 5" x 5" sterile template, the corners of each abdominal test area will be marked directly on the skin using a non-toxic skin marker. Four sampling sites will be numbered within each abdominal test area, on each side of the abdominal region. The positioning and numbering of the abdominal sampling sites are standard for all subjects. Sampling sites on the contra-lateral side of the abdomen will be numbered in a mirror-image orientation. The four sampling sites within each abdominal test area represent one baseline (pre-prep) site, one post-prep sample sites (10-minutes) and two sites will be designated as not sampled.

Prior to performing the Treatment Day baseline sample collection, a skin irritation assessment will be performed by the Investigator or designee trained by the Investigator.

If an irritation score of 1 is assigned for any individual skin condition at the Treatment Day baseline, the subject will be excluded from the treatment phase of the study. After abdominal test areas are marked and sample sites numbered, baseline samples will be collected from the appropriate site per the randomization schedule in each test area using the Williamson-Kligman scrub cup technique.

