7.4.1.3 Site and Sample Time Balance

Each groin and abdomen sample site is divided into four areas and two of these areas are sampled once – one at baseline and one at 10 minutes ± 30 seconds, and two areas will not be used. Therefore, for any groin or abdomen site there are 24 possible sampling orders.

The number of subjects required for a completely balanced block design for all factors at once (study products, left/right, and sampling order) is a multiple of 144 (3*2*24). The exact subject numbers may make it infeasible to provide a completely balanced block design, so the following priority order will be used for design:

1. Treatment combinations will always be applied in balanced blocks, with the block size being sufficient to preserve the ratio of 1:1:1 for all three study products.
2. Left/right balance will be preserved – each treatment will be applied an equal number of times to each side of the body.
3. Sampling orders will be assigned in blocks of 24 as much as possible. If the final number of subjects is not a multiple of 24 the remaining subjects will be assigned random non-duplicative sample orders from the 24 possible sample orders.
4. The blocking will be adjusted based on the final subject numbers to be as balanced as possible with respect to all three factors above at once, with priority using the order listed above.

The Investigator is responsible for ensuring that the randomization is followed. A basic outline of a randomization schedule for the abdominal and groin sites is provided in Appendix 22.4. The final randomization schedule will be prepared by the study statistician before the initial treatment.

Subjects will be identified by their initials, and a subject number.

- Randomized subjects will be assigned numbers ranging from 001 to a three digit number equal to the total number of test subjects needed (36 for the estimated numbers).

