7.5 Masking/Blinding

Treatment materials for the following treatment groups will be blinded with treatment codes A or B:

- Thermally treated cloth impregnated with 0.4% w/v octenidine dihydrochloride aqueous solution (test article)
- Thermally treated cloth impregnated with vehicle formulation (Vehicle control)

The 0.9% Saline Control cannot be blinded due to product application requirements and will be assigned to treatment code C.

The staff member(s) performing product applications, sample collections, and irritation assessments will not be blinded from the identification of treatment assignments. Staff member(s) performing bacterial enumeration will be blinded from the identification of all treatment assignments. The study staff performing the bacterial enumeration will not be involved in the study material application, or the collection of samples or skin irritation assessments. The Raw Data Sheet sections of the case report

form will be maintained separately (from the pages within the case report form which include study treatment identifications) during the conduct phase of the study. The study staff performing the bacterial enumeration will record counts directly onto the Raw Data Sheet pages of the case report form without accessing the subject study documentation folder containing the other case report form pages. The Raw Data Sheets will be compiled with the entire case report form after all data recording has been completed.

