10.3.2 Preparation of Groin Test Area on Treatment Day

The test site within the groin region (groin test area) is defined as the inner aspect of the upper thigh within and parallel to the inguinal crease below the groin. Using a 2" x 5" sterile template, the corners of each groin test area will be marked directly on the skin using a non-toxic skin marker. Four sampling sites will be numbered within each groin test area, on each side of the groin region. The positioning and numbering of the groin sampling sites are standard for all subjects. Sampling sites on the contra-lateral side of the groin will be numbered in a mirror-image orientation. The four sampling sites within

each groin test area represent one baseline (pre-prep) site, one post-prep sample sites (10-minutes), and two sites will be designated as not sampled.

Prior to performing the Treatment Day baseline sample collection, a skin irritation assessment will be performed by the Investigator or designee trained by the Investigator.

If an irritation score of 1 is assigned for any individual skin condition at the Treatment Day baseline, the subject will be excluded from the treatment phase of the study.

After groin test areas are marked and sample sites numbered, baseline samples will be collected from the appropriate site per the randomization schedule in each test area using the Williamson-Kligman scrub cup technique.

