10.3.3 Treatment Materials Application

Following baseline sample collection, randomly assigned contra-lateral test areas will be treated with the applicable treatment materials. The post-application sampling sites will be randomized among the sampling sites within a test area.

The treatment materials will be applied and the sampling configurations will be performed per the Randomization Schedule and the Study Material Treatment Application Instructions (Appendix 22.7). The duration of each application procedure will be recorded on the appropriate CRF.

All test materials, including packaging, will be weighed before and immediately following application (Appendix 22.7) and the weights will be recorded.

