17.2 Data Evaluability

Data sets analyzed

The full intent to treat (ITT) data set (all randomized subjects) will be used for the safety analysis.

A modified Intent to Treat (mITT) data set will be used for efficacy analyses. Inclusion for the mITT data set is evaluated for each body area (left and right for the groin and abdomen). For each body area, if the Treatment Day baseline bacterial count requirements are in the range of 3.00 to 5.50 \log_{10}/cm^2 , inclusive, on the abdomen and 5.00 to 7.50 \log_{10}/cm^2 , inclusive, on the groin, then the data from that body area are included in the mITT data set. Data collected will be excluded from Per Protocol data if the Treatment-Day baseline counts are outside the acceptable range. Analyses conducted on the mITT data set will also be conducted on the Per Protocol data set as supportive analyses when Per Protocol data are different from mITT data.

- For \log_{10} CFU/ cm^2 determinations, missing data will not be imputed for either mITT data or Per Protocol data and will be excluded from analysis.

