22.4 Randomization Scheme

Example Randomization Scheme – 30 second and 6 hour sites will not be used in this protocol.

Randomization Number	Subject Number	Treatment Area	Treatment Code Left Side	Treatment Code Right Side	Site 1	Site 2	Site 3	Site 4
R001		Ab / Groin / Both	A	C	Baseline	10 Minutes	30 Seconds	6 Hours
R002		Ab / Groin / Both	D	B	10 Minutes	Baseline	30 Seconds	6 Hours
R003		Ab / Groin / Both	A	B	30 Seconds	Baseline	10 Minutes	6 Hours
R004		Ab / Groin / Both	B	D	10 Minutes	Baseline	6 Hours	30 Seconds
R005		Ab / Groin / Both	C	B	10 Minutes	30 Seconds	6 Hours	Baseline
R006		Ab / Groin / Both	A	D	Baseline	6 Hours	10 Minutes	30 Seconds
R007		Ab / Groin / Both	B	C	30 Seconds	10 Minutes	Baseline	6 Hours
R008		Ab / Groin / Both	D	C	30 Seconds	Baseline	6 Hours	10 Minutes
R009		Ab / Groin / Both	D	A	30 Seconds	10 Minutes	6 Hours	Baseline
R010		Ab / Groin / Both	B	A	6 Hours	30 Seconds	10 Minutes	Baseline
R011		Ab / Groin / Both	C	A	Baseline	30 Seconds	6 Hours	10 Minutes
R012		Ab / Groin / Both	C	D	6 Hours	10 Minutes	Baseline	30 Seconds
R013		Ab / Groin / Both	D	A	Baseline	30 Seconds	10 Minutes	6 Hours
R014		Ab / Groin / Both	C	A	30 Seconds	6 Hours	10 Minutes	Baseline
R015		Ab / Groin / Both	C	B	6 Hours	Baseline	10 Minutes	30 Seconds
R016		Ab / Groin / Both	D	B	6 Hours	10 Minutes	30 Seconds	Baseline
R017		Ab / Groin / Both	A	C	10 Minutes	6 Hours	30 Seconds	Baseline
R018		Ab / Groin / Both	B	A	10 Minutes	30 Seconds	Baseline	6 Hours
R019		Ab / Groin / Both	B	C	6 Hours	30 Seconds	Baseline	10 Minutes
R020		Ab / Groin / Both	A	D	Baseline	10 Minutes	6 Hours	30 Seconds
R021		Ab / Groin / Both	A	B	30 Seconds	6 Hours	Baseline	10 Minutes

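### Baseline samplers work from a schedule that also shows each side's treatment code, so at least every saline side can be known before the baseline that gates and adjusts the primary analysis is taken

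*Protocol*

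**What the plan says.** **Where the baseline spot comes from.** For the abdomen (Protocol 10.3.1), "baseline samples will be collected from the appropriate site per the randomization schedule in each test area". For the groin (10.3.2), "After groin test areas are marked and sample sites numbered, baseline samples will be collected from the appropriate site per the randomization schedule".

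**What else the schedule carries.** Protocol 10.3: "The randomization schedule will designate the treatment to each side of the abdomen and groin". The illustration in Appendix 22.4 has one row per subject, with a column headed "Treatment Code Left Side", a matching column for the right side, and then the map of the four spots. Its status is limited. Protocol 7.4.1.3 states: "A basic outline of a randomization schedule for the abdominal and groin sites is provided in Appendix 22.4". The final schedule is to be prepared before the first treatment.

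**Who is blinded.** Protocol 7.5: "The staff member(s) performing product applications, sample collections, and irritation assessments will not be blinded from the identification of treatment assignments". Those who count the plates are blinded. Test article and vehicle carry codes A or B, and saline is openly code C. Under 7.5.1 the A/B key is held in sealed envelopes by site quality assurance, and under 9.5 the cloths arrive labelled only A or B.

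**Order of events.** Protocol 10.3.3: "Following baseline sample collection, randomly assigned contra-lateral test areas will be treated with the applicable treatment materials".

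**What the baseline does.** If a body area's baseline is in range (3.00 to 5.50 log10 on the abdomen, 5.00 to 7.50 on the groin), "then the data from that body area are included in the mITT data set" (Protocol 17.2; SAP 6.1 agrees). The baseline is also the covariate in the primary regression (Protocol 17.3.1; SAP 7.4.1) and the starting value for the exploratory log reduction (SAP 7.1.2).

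**The concern.** A baseline measurement should be taken by someone who does not know what that site will receive. Here the document that tells the sampler where to place the cup also tells them which code goes on which side, although the code is not needed until product is prepared and applied.

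The sample depends on the operator: two one-minute manual scrubs with a rubber policeman (Protocol 10.3.5). If recovery differed systematically between sides because the sampler knew what was coming, the mITT gate and the primary covariate would both become partly treatment-dependent. Blinded counting cannot undo a difference created at the skin. Masking after treatment would not help either, because the issue is when allocation is revealed.

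**Working it through.** The documents give no figure for this point, so the check is a comparison of sections followed by an illustrative calculation.

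**1. Is allocation visible before baseline?** The spot is read from the schedule (10.3.1, 10.3.2). The schedule holds the side assignment (10.3). Samplers are not blinded (7.5). Product follows baseline (10.3.3). Neither document separates the spot list from the codes, releases the codes in stages, or uses a separate blinded baseline sampler. So yes, as written.

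**2. How many subjects have a known saline side?**
- Planned count reproduced: 36 subjects × 2 treatments / 3 products = 24 sites per treatment per region, as stated.
- SAP 3.3 splits subjects 12 A/B, 12 A/C and 12 B/C. Subjects with a saline side: 12 + 12 = 24 of 36. Every saline site is in this group.

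**3. Which comparisons are exposed?**

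| Reading | Sampler knows | IP vs saline | IP vs vehicle |
|---|---|---|---|
| A/B key sealed (7.5.1, 9.5) | Saline side against an unidentified cloth | Exposed | Expected shift zero |
| Identities known (7.5 taken literally) | All three products | Exposed | Exposed |

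On the first reading, a cloth-versus-saline tendency affects A and B alike (12 A/C and 12 B/C subjects), so it cancels in expectation between test article and vehicle.

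**4. Size of a shift.** Let d be the mean spurious baseline difference (test-article side minus control side) and b the slope of post-treatment count on baseline.
- Primary, baseline-adjusted contrast: shift = b × d.
- Exploratory log-reduction contrast: shift = d.
- Assumed d = 0.1 to 0.2 and b = 0.2 to 1.0: from 0.2 × 0.1 = 0.02 to 1.0 × 0.2 = 0.20 log10.
- Against the margin: 0.02 / 1.2 = 1.7% to 0.20 / 1.2 = 16.7%. The sign follows d and could go either way.

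The documents give neither d nor b. The SAP's mock Tables 6 and 7 cannot supply b. Using slope = (SD_base² + SD_post² − SD_red²) / (2 × SD_base²), they imply 0.18, 1.18 and −0.69 for A, B and C, which is not a usable estimate.

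**5. Would the planned baseline ANOVA catch it?** Taking the mock baseline SD of 0.53 purely as an assumption, an unpaired contrast of 24 vs 24 has SE = 0.53 × √(2/24) = 0.15. A difference of 0.1 to 0.2 is then about 0.7 to 1.3 SE and could easily pass. The SAP model's random subject effect should improve this somewhat. Neither document says what follows if an imbalance is found.

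**The case against.** The case against is substantial, and most of it limits the point.

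- **Product identity.** A reader might infer that samplers know which side will receive the test product. The documents do not establish this. The row shows letters, the cloths are labelled A or B, and the key is sealed. Protocol 7.5 points the other way, and the text does not settle which describes practice.
- **Overall success.** SAP 7.4.1 requires superiority over both controls in both regions. A bias confined to IP vs saline cannot by itself produce a successful study. This stands for the sealed-key reading.
- **The gate.** A reader might infer that a sampler could steer a borderline site into mITT. Plates are read by blinded staff after 72 ± 4 hours of incubation (Protocol 10.3.5), and qualification comes after treatment (Appendix 22.2). A sampler cannot know which sites are borderline, and the range has an upper limit as well as a lower one. Only a general tendency in recovery could affect the gate.
- **Safeguards.** The spot is fixed by the schedule; the cup area, volumes and scrub time are standardized; counting is blinded; a baseline ANOVA is planned. These narrow the exposure to how the scrub and skin score are carried out, but do not remove it.
- **Layout.** Appendix 22.4 is an example, with an unused code D and unused time points. The working sheet may differ. Even so, 10.3 to 10.3.2 have a single schedule carrying both items, whatever its layout.
- **Skin score.** SAP 7.4.2 says subjects with irritation before baseline are not randomized, which suggests that check may precede allocation. The baseline sample cannot, because its spot comes from the schedule.
- **Purpose.** This is an unpowered phase 2 study meant to inform later designs (Protocol 17.1). That lowers the stakes, but a sound procedure would carry forward.

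**Conclusion.** The point holds as an avoidable opportunity for bias. As written, allocation can be seen before the baseline scrub, and at minimum every saline side is known in advance: 24 of 36 subjects under the planned split. If A and B stay masked, only IP vs saline is exposed. If samplers know the codes, IP vs vehicle is exposed too. Protocol 7.5, 7.5.1 and 9.5 must be reconciled to say which applies.

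The possible shift in the primary contrast is 0.02 to 0.20 log10, resting entirely on assumed d = 0.1 to 0.2 and b = 0.2 to 1.0. The true d may be zero. It would be too strong to say that the baseline or the treatment effect is biased; nothing in the documents shows that. The point merits action because the change is cheap, not because harm has been shown.

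**What to change.** Issue the schedule in two parts.

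1. **Spot list**, used for the pre-treatment skin score and baseline sampling: subject number and the Baseline/10-minute spot map only.
2. **Code section**, sealed or folded over: left and right treatment codes, opened only after the skin score is recorded and the baseline samples from all the subject's test areas are in tubes. Record the opening time on the CRF.

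Amend Protocol 10.3.1, 10.3.2, 10.3.3 and the Appendix 22.4 layout. In the same amendment, reconcile 7.5 with 7.5.1 and 9.5 on whether samplers know A from B.

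**Cost.** A reformatted schedule and one time entry per subject, with no added staff, visits or samples. The real inconvenience is saline. Appendix 22.7 uses one cloth per anatomical region, so a saline side needs up to two bags. These would be wetted, rolled and weighed after baseline sampling, or prepared beforehand for every subject with some waste. For 36 subjects treated in both regions, that is 36 × 2 = 72 bags prepared, 24 × 2 = 48 used and 24 discarded.
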